Title :Efficacy and Safety of Nadroparin Calcium-Warfarin Sequential
Anticoagulation in Portal Vein Thrombosis in Cirrhotic Patients: A
Randomized Controlled Trial

NCT number: NCT04173429

Date of the Document:2020-7-3

Study Protocol

All patients admitted at the Gastroenterology Department of the Qilu Hospital of Shandong University in China, who were diagnosed with PVT, were prospectively and consecutively evaluated in this study. The inclusion criteria were the following: age between 18 and 75 years, liver cirrhosis diagnosis based on clinical, laboratory and imaging studies, PVT diagnosed by abdominal contrast-enhanced computed tomography (CT), contrast-enhanced magnetic resonance imaging (MRI) or portal angiography. The exclusion criteria were the following: cavernous transformation of the portal vein, uncontrolled active bleeding, platelet count lower than $10 \times 10^9/L$, creatinine more than $170 \mu\text{mol/L}$, ongoing or received antithrombotic/thrombolytic treatment, primary thrombophilia, Budd-Chiari syndrome, pregnancy or breast-feeding period, severe cardiopulmonary diseases, severe systemic infection or sepsis, and inability to sign the informed consent.

Eligible patients were randomly divided into two equal groups: NWS therapy group and control group. Randomization was performed using a computer-based random number table procedure. Randomly generated serial numbers were placed in opaque envelopes. Patients and clinicians carrying out the interventions were not blinded, while clinicians performing the imaging assessments and data analysis were blinded to the group allocation and patients' coded data.

Procedure

The NWS therapy group received a subcutaneous injection of nadroparin calcium every 12 h for 1 month followed by an oral administration of warfarin for 5 months.

Warfarin was started at least 5 days before nadroparin calcium was stopped. International normalized ratio (INR) was monitored every 3-4 days and the daily dose of warfarin was carefully adjusted by the increase or decrease of 0.75 mg until the INR target level of 2-3 was achieved. Patients in the control group did not receive any anticoagulation treatment.

All patients underwent gastroscopy to evaluate the degree of varices and received endoscopic ligation or sclerotherapy if necessary. Patients in the NWS therapy group initiated the anticoagulation therapy after endoscopic therapy.

Imaging studies

PVT assessed by imaging examination appears as the absence of flow in part or all the lumen of the splenoportomesenteric axis, including portal vein trunk and branches, SV or SMV, with the presence of solid material in the vein. The degree (partial occlusion or complete occlusion) and extension (portal vein only or extension into the SV and/or SMV) of PVT were also evaluated in all the enrolled patients at admission by upper abdominal contrast-enhanced CT or MRI or portal angiography. The assessments of thrombosis were based on a published study(22). For each venous segment, the vein and residual patent lumen were outlined at the level of the maximum thrombosis. Total lumen area and patent lumen area were calculated with commercially available software. The degree of thrombus occlusion was estimated as a percentage by $\text{thrombosis area}/\text{total lumen area} \times 100\%$ (22). The extension of thrombosis was referred to the involved segments of the portal vein system, regardless of whether thrombosis was formed in the portal vein only or extended into the SMV and/or SV(23, 24).

Complete and partial thrombosis were defined as equal or greater than 90% and less than 90% thrombotic material presence within vessels, respectively. Although the imaging assessments were performed by a single reader, the bias is minimized as the calculated assessments are objective.

Follow-up

Follow-up visits were scheduled at the 0th and 6th month, and included clinical, laboratory and imaging evaluation. The follow-up started at the diagnosis of PVT, defined as starting on the date of the first radiological imaging documenting PVT, and stopped in January 2020 or the day of death or the date of the last visit at 6th month. Liver function and cirrhosis severity were assessed by Child-Pugh score and the Model for end-stage liver disease (MELD) score respectively at the 0th and 6th month.

Bleeding episodes were assessed every month by phone call. Once a severe bleeding episode occurred, the anticoagulation treatment was stopped immediately and endoscopic therapy was performed if necessary.

Outcomes and definitions

The primary outcome was the overall recanalization rate, both complete and partial. The secondary outcomes were bleeding rates, consisting of rates of hematemesis, melena, epistaxis, injection-site hemorrhage and other bleeding events.

Portal vein recanalization was evaluated on the basis of imaging examination. Complete recanalization was referred to the complete disappearance of the thrombus in the portal vein trunk, at least one of the two intrahepatic portal vein branches, SMV and SV. Partial recanalization was defined as a more than 50% reduction of the thrombus,

with the thrombus not extending to other veins. No response or stable thrombosis was defined when the thrombus maintained the same dimension, or achieved a less than 50% decrease or less than 30% increase on cross section. Progression was defined as more than 30% increase of the thrombus than before or thrombus extended to unaffected segments of the splenoportomesenteric axis (Fig. 1).

Group size calculation

The overall recanalization rate of the PVT at the 6th month was chosen as the primary outcome to calculate the size of the groups. Based on previous studies (25), assuming a 30% difference in the overall recanalization of PVT at 6th month between the anticoagulation (70%) and control group (40%), 5% α and 20% β error, 27 patients were needed in each group. Considering a 10% dropout rate, 30 patients should be included in each group.

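### Bleeding follow-up has no planned time after the last dose, and closes before warfarin ends whenever the start is delayed enough

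*Protocol*

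**What the plan says.** Protocol, Procedure. NWS patients receive a "subcutaneous injection of nadroparin calcium every 12 h for 1 month followed by an oral administration of warfarin for 5 months". The two drugs overlap: "Warfarin was started at least 5 days before nadroparin calcium was stopped". Every patient in both arms has gastroscopy and "received endoscopic ligation or sclerotherapy if necessary". On the order of events in the treated arm: "Patients in the NWS therapy group initiated the anticoagulation therapy after endoscopic therapy". The time from diagnosis or randomisation to the first dose is not given.

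Protocol, Follow-up. The time origin is the diagnostic scan: "The follow-up started at the diagnosis of PVT, defined as starting on the date of the first radiological imaging documenting PVT". The end is set by the rule that follow-up "stopped in January 2020 or the day of death or the date of the last visit at 6th month". On contacts: "Follow-up visits were scheduled at the 0th and 6th month". Bleeding is asked about in a monthly phone call, and no separate end date is set for those calls. The same section says what happens to anticoagulation after a severe bleed, again without saying for how long that provision runs.

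Protocol, Outcomes and definitions. Bleeding rates are the secondary outcome, with no time window. The SAP adds none.

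**The concern.** A course of nominally six months is placed in a six-month observation window, and the window opens first. The scan that starts the clock is also what makes the patient eligible, so randomisation, gastroscopy and any endoscopic treatment come on or after that date, and the first dose follows them. Whatever time these steps take is unexposed time at the front of the NWS arm's window. At the back there is little or no room left for the end of the course, and none is planned for the period after it.

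At stake is the trial's only named secondary outcome, in a trial whose title promises safety as well as efficacy. The planned size is 30 patients per arm, so a handful of bleeds missed late in treatment or shortly after it could change how the safety result reads. The primary outcome, recanalization on imaging at month 6, is not affected.

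**Working it through.** The plan gives no calculated figure on this point, so the check is calendar arithmetic on its stated durations.

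**Inputs**
- Treatment: 1 month of nadroparin, then 5 months of warfarin (Protocol, Procedure).
- Overlap O: at least 5 days (Procedure). The text does not say whether the 5 warfarin months run from the end of nadroparin or from the first warfarin dose, so both are worked.
- Window F: diagnostic scan to month-6 visit (Protocol, Follow-up). With a month of 365.25/12 = 30.44 days, F = 6 × 30.44 = 182.6 days, and 5 months = 152.2 days.
- Delay D, from scan to first dose: not in the documents. Assumed at 0, 7, 14 and 28 days.
- End of the bleeding calls: taken as the end of follow-up. This is inferred from the general stop rule, since the calls have no end date of their own.

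**Formulas**
- Count A, 5 months from the end of nadroparin: last dose at D + F. Uncovered warfarin = D. Days covered after the last dose = 0.
- Count B, 5 months from warfarin start: last dose at D + F − O. Uncovered warfarin = max(0, D − O). Days covered after the last dose = max(0, O − D).

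**Results** (in brackets, share of the 152.2 warfarin days)

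| Assumed delay D | Count A, uncovered | Count B, O = 5, uncovered | Count B, O = 10, uncovered |
|---|---|---|---|
| 0 days | 0 | 0 | 0 |
| 7 days | 7 (4.6%) | 2 (1.3%) | 0 |
| 14 days | 14 (9.2%) | 9 (5.9%) | 4 (2.6%) |
| 28 days | 28 (18.4%) | 23 (15.1%) | 18 (11.8%) |

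**Time after the last dose.** Under count A none is covered at any D. Under count B with O = 5, the covered time is 5 days at D = 0 and none once D reaches 5. With O = 10 it is 10 days at D = 0 and 3 days at D = 7. These few days are a by-product of how the overlap is counted, not a planned safety period.

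**Effect on the comparison.** Suppose bleeding occurs at a constant rate r1 on anticoagulation and r0 off it. When the course reaches or passes the end of the window (any D under count A, D of at least O under count B), the NWS arm has F − D exposed days in the window. The average excess over control is then (r1 − r0) × (F − D)/F, so the excess shrinks by the fraction D/F: 7/182.6 = 3.8%, 14/182.6 = 7.7%, 28/182.6 = 15.3%. The direction requires r1 > r0, which the documents do not state.

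**The case against.** The strongest reply is that nothing need be lost. Patients are enrolled as inpatients and the thrombus is assessed at admission, so gastroscopy in the same admission is possible, and ligation or sclerotherapy is given only where needed. With no delay, or under count B with a delay no longer than the overlap, all warfarin time lies inside the window. This stands. A reader might infer that the end of the warfarin course is certainly unobserved, but the documents do not support that. It depends on a delay they do not give and on a count they do not define.

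Second, the calls and the severe-bleeding provision carry no expiry date. A reader might infer that the provision lapses while patients are still taking warfarin. Its place under Follow-up does not establish that, and its wording ties it to treatment. The end of the calls at month 6 is likewise an inference, though a reasonable one, because no later contact appears in either document.

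Third, both arms share the same clock and both have gastroscopy, so comparing bleeding over six months from diagnosis is a legitimate intention-to-treat comparison. That also stands. It answers a different question from bleeding during and shortly after anticoagulation. A reader might also count the unexposed wait at the front and the cut-off at the back as two biases. In a fixed window they are one: D unexposed days take the place of D exposed days.

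Finally, it is tempting to say that patients needing repeated endoscopic sessions have the largest gap. The documents describe no repeat sessions and do not say that anticoagulation waits for a full course of them.

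None of this supplies planned bleeding collection after the last dose.

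**Conclusion.** The concern holds in two parts of different strength.

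The first does not depend on the size of the delay. As written, the plan has essentially no bleeding observation after the last dose for a patient who completes treatment: none under one count of the warfarin months, and at most the overlap less the delay under the other. It rests on the calls ending with follow-up.

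The second is conditional. Warfarin exposure falls after the close of follow-up if the delay exceeds zero (count A) or exceeds the overlap (count B). Over assumed delays of 0 to 28 days this is 0 to 28 days, or 0 to 23 days with a 5-day overlap. Over the same delays the dilution of any true excess is at most about 15%, if bleeding rates are constant and higher on treatment. That is modest, but it runs towards showing no excess in NWS.

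The January 2020 stop could shorten observation further for patients enrolled late. Enrolment dates are not given, so its effect cannot be sized.

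**What to change.** - Keep the month-6 imaging for the primary outcome as it is.
- Continue the monthly bleeding calls in NWS to the end of planned anticoagulation plus a stated interval. Follow control patients for the same length of time from a matching start: completion of gastroscopy, or of endoscopic therapy where it was given. This point exists in both arms. Setting the length by planned rather than actual treatment keeps it from depending on who stops early.
- State in the SAP that between-arm bleeding rates are compared over this common window.
- Reconcile the Procedure and Follow-up sections on three matters: the origin of month 0, how the five warfarin months are counted given the overlap, and how long the severe-bleeding provision applies. Which clinical rule is right is for the investigators.
- If data collection has already closed, which the July 2020 document date and the January 2020 stop suggest, report the dates of first dose, last dose and last contact, and add a sensitivity analysis of bleeding based on exposure time.

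The cost is one or two more calls per patient, a few lines of wording, and a slightly later last contact. If collection is closed, the cost is tabulating dates and one extra analysis.

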Title :Efficacy and Safety of Nadroparin Calcium-Warfarin Sequential
Anticoagulation in Portal Vein Thrombosis in Cirrhotic Patients: A
Randomized Controlled Trial

NCT number: NCT04173429

Date of the Document:2020-7-3

Statistical Analysis Plan

Statistical analysis was performed using the statistical software IBM SPSS Statistical 24.0. The analysis of the outcomes between NWS therapy group and control group was conducted by both intention-to-treat (ITT) and per-protocol (PP) analysis. All eligible patients were analyzed by ITT analysis, and patients who did not violate the protocol were analyzed by PP analysis.

Quantitative variables were expressed as the mean \pm standard deviation (SD), while qualitative variables were expressed as percentages. Quantitative variables were compared using Student's *t*-test or Wilcoxon-rank sums test, and categorical variables were compared using chi-squares or Fisher's exact test, as appropriate. Univariate and multivariate logistic regression analysis were performed to find significant end point predictors for recanalization. A two-tailed *p*-value <0.05 was considered statistically significant.

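### A month-6 comparison of MELD or Child-Pugh under the SAP's general rule would read warfarin's INR effect, present in the NWS group only, as liver deterioration

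*Protocol*

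**What the plan says.** - **When the scores are taken.** The protocol, under Follow-up, has liver function and cirrhosis severity "assessed by Child-Pugh score and the Model for end-stage liver disease (MELD) score respectively at the 0th and 6th month".
- **Treatment in the NWS group.** Under Procedure, nadroparin is given "for 1 month followed by an oral administration of warfarin for 5 months", and the warfarin dose is adjusted "until the INR target level of 2-3 was achieved". The two drugs overlap: "Warfarin was started at least 5 days before nadroparin calcium was stopped".
- **Treatment in the control group.** "Patients in the control group did not receive any anticoagulation treatment".
- **Early stopping.** Under Follow-up: "Once a severe bleeding episode occurred, the anticoagulation treatment was stopped immediately".
- **Outcomes.** Outcomes and definitions lists recanalization as primary and bleeding rates as secondary. Neither liver score is listed.
- **Analysis.** The SAP's one rule for measurements of this kind begins "Quantitative variables were compared using Student's" and offers the t-test or the Wilcoxon rank-sum test. Categorical variables get a chi-square or Fisher's exact test. Neither document gives a purpose for the month-6 scores or says how INR is to be handled in them.

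**The concern.** A score that includes INR measures liver function only while nothing else is moving INR. At month 0 that is so in both groups, because earlier or ongoing antithrombotic treatment is an exclusion. At month 6 it may fail in the NWS group, where the study drug is meant to raise INR, and it holds in the controls. The distortion is therefore confined to one arm and always points towards apparent worsening. Randomization does not remove it, and neither does adjusting for the month-0 score, because it arises after baseline. Using change from month 0, or looking at change within the NWS group alone, carries the same bias.

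At stake is how the liver scores are read. A comparison could report that anticoagulation harms the liver in cirrhosis when only the drug's effect on INR has been measured, or it could hide a real improvement.

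**Working it through.** The documents give no figure for either score, so there is nothing to reproduce. The check takes timing first, then size.

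**Is the month-6 sample likely to be on warfarin?** One month of nadroparin plus five months of warfarin runs to about month 6 from the start of treatment. Two things shift this:
- Starting warfarin at least 5 days before nadroparin ends could finish a 5-month course a few days before month 6.
- Follow-up is counted from the first imaging that shows thrombosis, while anticoagulation starts later, after endoscopic therapy. If month 6 is counted from that imaging, treatment ends later relative to the visit.

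The second makes on-treatment sampling more likely. Stopping after severe bleeding makes it less likely for some patients. The fraction at target INR when sampled cannot be derived from the documents, so it is varied below.

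**Inputs**
- From the documents: INR target 2-3; 27 per group ("27 patients were needed in each group"); two-sided 0.05; unadjusted test.
- Assumed: MELD INR term 11.2 × ln(INR); INR without warfarin 1.3 (range 1.2-1.7); MELD SD 5 (range 3-6); fraction *f* of NWS at the stated INR of 1, 0.5 or 0.25.

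**Shift per patient** = 11.2 × ln(INR on warfarin / INR without)
- 1.3 to 2.0: 4.82
- 1.3 to 2.5: 7.32
- 1.3 to 3.0: 9.37
- Smallest, 1.7 to 2.0: 1.82
- Largest, 1.2 to 3.0: 10.26

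**Shift in the NWS mean** = *f* × shift per patient

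| *f* | INR 2.0 | INR 2.5 | INR 3.0 | range over baseline 1.2-1.7 |
|---|---|---|---|---|
| 0.5 | 2.41 | 3.66 | 4.68 | 0.91 to 5.13 |
| 0.25 | 1.21 | 1.83 | 2.34 | 0.46 to 2.57 |

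**Chance of p<0.05 with no true difference.** Simulation of 40,000 trials, 27 per group, two-sample t-test, shift applied at random to a fraction *f* of the NWS group:

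| Scenario | SD 3 | SD 5 | SD 6 |
|---|---|---|---|
| 1.3 to 2.5, *f* = 1 | ≥0.99 | ≥0.99 | ≥0.99 |
| 1.3 to 2.5, *f* = 0.5 | 0.914 | 0.648 | 0.525 |
| 1.3 to 2.5, *f* = 0.25 | 0.413 | 0.219 | 0.172 |
| 1.7 to 2.0, *f* = 0.25 | 0.084 | 0.064 | 0.057 |

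A rank test in place of the t-test gives about 60% and 18% where the t-test gives 65% and 22%.

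**Hand check.** With shift *d* in a fraction *f*, the NWS variance is SD² + *f*(1−*f*)*d*². The t critical value on 52 df is 2.007.
- 1.3 to 2.5, *f* = 0.5, SD 5: variance 25 + 0.25 × 53.64 = 38.41. Standard error √((25 + 38.41)/27) = 1.532. Ratio 3.662/1.532 = 2.390. Φ(2.390 − 2.007) = 0.649, in line with 0.648.
- 1.3 to 2.0, *f* = 0.5, SD 5: variance 25 + 0.25 × 23.28 = 30.82. Standard error √((25 + 30.82)/27) = 1.438. Ratio 2.412/1.438 = 1.678. Φ(1.678 − 2.007) = 0.371.

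So at the bottom of the target range with the central baseline INR, the false-positive rate is still about 37% with half of NWS at target.

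**Child-Pugh.** If coagulation is scored on INR with cut-offs at 1.7 and 2.3 (assumed), an INR of 2-3 adds 1 to 2 points to a patient who would otherwise be below 1.7.

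**The case against.** The strongest reply is that this criticises an analysis nobody has planned. The scores are assessed but are not outcomes, the SAP ties its NWS-versus-control analysis to the outcomes, and its sentence on quantitative variables may be meant only for baseline tables. That is a fair reading, and it is why the point is conditional. But a scheduled month-6 assessment has little use other than comparison between arms or over time, and the SAP neither excludes that nor guards it.

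A second reply is that the size rests on assumed inputs, so false-positive rates run from about 6% to at least 99%. This stands: no single figure should be quoted as the expected rate. The figures are also for a month-6 comparison; the SD of change from month 0 may differ and was not modelled. The direction depends on none of the assumed values, only on the scores containing INR.

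A third reply is timing. Both documents are dated July 2020 and the protocol ends follow-up in January 2020, so warfarin status at sampling can no longer be recorded prospectively. This also stands, and limits that part of the remedy to retrieval from patient records.

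**Conclusion.** The concern holds in its conditional form. If month-6 MELD or Child-Pugh, or the change from month 0, is compared between groups under the SAP's general rule, the result is biased towards apparent deterioration on NWS. The bias is large if half or more of the NWS group is at about INR 2.5 when sampled, and negligible if few are at target and untreated INR is already high. This rests on the standard definition of the scores and on the assumed weight, untreated INR, SD and fractions. It affects only the reading of the liver scores, so it is a correction that should be made, not one on which the trial's main conclusions depend.

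**What to change.** Add to the SAP that any month-6 between-group comparison of liver function uses measures without INR, adjusted for the month-0 value: bilirubin, albumin, creatinine, and a MELD that either omits INR or holds it at its pre-treatment value. Report standard MELD and Child-Pugh at month 6 descriptively only, next to the month-6 INR and whether the patient was on warfarin when sampled, taken from records where it was not captured.

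The cost is a short SAP addition, recalculation from laboratory values already needed for the scores, and a record check for warfarin status. Sample size, visits and treatment do not change. The drawbacks are that a modified MELD is less familiar, and that dropping or freezing INR discards real change in synthetic function, including in controls, where INR remains a valid marker. Keeping the standard scores in the descriptive tables limits that loss.

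### The stated 27 patients per group does not give 80% power for 70% versus 40%: those inputs need about 42, and 27 gives about 60%

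*Protocol*

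**What the plan says.** The protocol's "Group size calculation" section sizes the trial on overall recanalization at month 6, "assuming a 30% difference in the overall recanalization of PVT at 6th month", with rates of 70% on anticoagulation and 40% in controls. It then gives the error rates and the result: "5% α and 20% β error, 27 patients were needed in each group". The allowance for losses follows: "Considering a 10% dropout rate, 30 patients should be included in each group".

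The section names no formula, software or sidedness. The sidedness comes from the SAP: "A two-tailed *p*-value <0.05 was considered statistically significant". For the test, the SAP says that "categorical variables were compared using chi-squares or Fisher's exact test, as appropriate". The protocol's randomization text gives the allocation: "Eligible patients were randomly divided into two equal groups".

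**The concern.** Detecting 70% against 40% with 80% power at a two-sided 5% level normally takes around 40 patients per group. A figure of 27 is about a third below that, which is too far to be rounding or choice of formula.

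This paragraph is the only justification for the size of the trial, and it concerns the primary outcome. If the claimed 20% type II error is really about 40%, the trial would miss the effect it was designed to find about two times in five. A non-significant comparison could then be taken as evidence from an adequately powered trial when it is not.

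**Working it through.** **Inputs.** p₁ = 0.70, p₂ = 0.40, difference d = 0.30, α = 0.05, power 0.80 and 10% dropout come from the protocol's sample-size section. The two-sided level comes from the SAP, and 1:1 allocation from the protocol's randomization text. The mean rate is p̄ = 0.55, so 2p̄(1−p̄) = 0.495. Also p₁(1−p₁) + p₂(1−p₂) = 0.21 + 0.24 = 0.45. The normal quantiles are 1.960 (two-sided 5%), 1.645 (one-sided 5%) and 0.842 (80% power).

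**The plan's own figures.** The dropout step reproduces: 27/(1 − 0.10) = 30. The base figure of 27 does not reproduce under any method tried.

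**Sample size per group.**

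- Pooled: n = [1.960·√0.495 + 0.842·√0.45]² / 0.30² = (1.379 + 0.565)² / 0.09 = 41.97, so 42.
- Unpooled: n = (1.960 + 0.842)² × 0.45 / 0.09 = 39.2, so 40.
- Variance at the mean rate: n = (1.960 + 0.842)² × 0.495 / 0.09 = 43.2, so 44.
- Arcsine: h = 2·arcsin√0.70 − 2·arcsin√0.40 = 0.613; n = 2(1.960 + 0.842)² / h² = 41.8, so 42.
- Continuity-corrected: n = (41.97/4)·[1 + √(1 + 4/(41.97 × 0.30))]² = 48.4, so 49.

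Replacing 1.960 by 1.645 gives the one-sided 5% results: unpooled 30.9 (31), pooled 32.9 (33), arcsine 32.9 (33), mean-rate variance 34.0 (35), continuity-corrected 40. The smallest figure under any variant is 31.

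**Power at the planned sizes.** For the pooled normal approximation at n = 27:

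- standard error under the null = √(0.495/27) = 0.1354
- standard error under the alternative = √(0.45/27) = 0.1291
- power = Φ[(0.30 − 1.960 × 0.1354)/0.1291] = Φ(0.268) = 60.6%

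The exact figures sum the probabilities of all rejecting outcomes over the two binomial distributions. All figures are two-sided at 5%:

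| Method | 27 per group | 30 per group, no dropout |
|---|---|---|
| Unpooled normal | 64.2% | 68.8% |
| Arcsine | 61.5% | 66.0% |
| Pooled normal | 60.6% | 65.3% |
| Exact, uncorrected chi-square | 58.6% | 66.3% |
| Continuity-corrected normal | 49.3% | 54.8% |
| Exact, Fisher | 48.1% | 56.1% |

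As a check on the corrected size, 42 per group gives 82.8% exact power with the uncorrected chi-square test and 76.4% with Fisher's test. Fisher's test reaches 80.0% at 48 per group.

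**What 27 would correspond to.** In the pooled formula, 27 per group is the answer for 70% versus 40% at 60% power, or for 77% versus 40% at 80% power. The second is a 37-point difference. The documents state neither.

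**Precision.** At 27 per group and the assumed rates, the 95% confidence interval for the difference has a half-width of 1.960 × 0.1291 = 0.253, about 25 percentage points.

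**The case against.** No defence recovers 27, but several points limit how the finding should be put.

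- **Sidedness.** The sample-size section is silent, so the calculation may have been one-sided. The SAP's two-tailed rule speaks against that, and one-sided formulas still need at least 31.
- **No single correct n.** The plan names no formula, so 42 is the pooled value within a 40–49 range, and power at 27 runs from 48% to 64%. This stands, but no value in that range supports 80%. The 77% detectable rate is likewise a pooled result; the unpooled formula gives about 75%.
- **Which number is wrong.** The slip could lie in a stated rate rather than in 27, and the source cited for the assumptions is not available here. This stands. What is certain is that the inputs and the 27 do not agree.
- **Number analysed.** The SAP's intention-to-treat analysis covers all eligible patients, so up to 30 per group may count. Even with no outcomes missing, that gives 65–69% with the normal (not continuity-corrected) and exact chi-square methods.
- **Fisher's test.** At 27 per group the expected cell counts are 27 × 0.55 = 14.9 and 27 × 0.45 = 12.2, so small counts give no reason to use it. This stands, and the headline figure therefore rests on the chi-square and pooled normal results.
- **Consequence.** Type I error is not inflated: exact chi-square size at 27 per group is 4.3% to 4.7% for common rates of 55% and 40%. A significant result is not invalidated. The protocol ends follow-up in January 2020 at the latest and both documents are dated July 2020, so enrolment can no longer change. That limits the remedy to the wording; it does not make the stated power true.

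**Conclusion.** The point holds. On the trial's own rates and error levels, with the SAP's two-sided test and equal groups, 80% power needs about 42 evaluable patients per group (40–49 across standard formulas). The planned 27 gives about 59–61% power with the chi-square or pooled normal method, so type II error is about 40%, twice what is claimed. If Fisher's test were used, type II error would be about 52% at 27 per group and 44% at 30.

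This rests on independent binary outcomes and a simple comparison of two proportions; the documents describe no design feature that would lower the requirement. The defect concerns power and precision, and so the reading of a non-significant result. It must be corrected because a central numerical claim about the design is not true as written.

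**What to change.** Rewrite the sample-size paragraph so that its numbers agree, and name the formula, the test and the two-sided level. Given the dates, the workable version keeps 30 per group and restates the power, for example:

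> With 30 patients enrolled and 27 evaluable per group, a two-sided 5% comparison has about 60% power to detect recanalization of 70% versus 40% (pooled normal approximation), and 80% power only for about 77% versus 40%. Eighty per cent power for 70% versus 40% would have required 42 evaluable patients per group, or 47 after allowing for 10% dropout (42/0.9 = 46.7).

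If the trial's records show that a different rate or power entered the calculation, state that input and say that it replaces the published one.

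The report should present the difference in recanalization with its 95% confidence interval and should not treat a non-significant result as evidence of no effect.

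Separately, the SAP should say which test is primary, because the choice between uncorrected chi-square and Fisher moves power by about 10 points. The expected counts support the uncorrected chi-square test. The reason given should be those counts and not the gain in power, and a choice made after follow-up ended should be labelled as such.

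The cost is a few sentences and a less favourable power figure. No further patients are needed.
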